Dietary patterns research has overcome the limitations of single nutrient research to a large extent but not completely. Methodological issues have hindered a wider translation of findings from dietary patterns research, the major critique being lack of consistency and scientific rigor in the methods. In Aim 1a we will utilize a standardized methodology to evaluate the associations of the 8 dietary patterns with all-cause mortality as a marker for overall health and with CRC risk, adjusting for the same set of potential confounders, and further investigate in Aim 1b several inflammatory markers (CRP, IL6, TNFR, and adiponectin) and hyperinsulinemia (C-peptide) as mediators of the association between dietary patterns and CRC risk. This will provide an unprecedented opportunity to evaluate the consistency of evidence for the benefits of diet quality for overall health and for CRC prevention, supported by strong epidemiological methods and biological plausibility.

Methodological Approach

Study Population: The NHS was established in 1976 as a prospective cohort of 121,701 U.S. registered female nurses who were aged 30 to 55 years at enrollment.^{61,62} The HPFS was initiated in 1986 as a prospective cohort of 51,529 U.S. male health professionals who were aged 40 to 75 years.⁶³ Blood samples were collected from subpopulations of the NHS (n=32,826) in 1989-1990 and HPFS (n=18,225) from 1993 to 1994, using similar protocols for all cohorts.^{64,65}

Assessment of dietary data: Dietary data are updated every four years in the NHS (since 1980), NHS-II (since 1991) and in the HPFS (since 1986) with a validated semi quantitative food frequency questionnaire (FFQ) assessing habitual intake of foods and beverages over the preceding year. Participants reported how often, on average, they consumed each food of a standard portion size.⁶⁶⁻⁶⁸ We will use average dietary data cumulatively across the multiple FFQs, to reduce within-subject variation and best represent long-term diet.^{69,70}

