outcomes have been collected through participants, next-of-kin, or death certification. For any report of CRC, we seek written permission from study participants or next-of-kin to review their medical records. Study physicians review these records and successfully confirm 97% of reported CRC. The National Death Index is used to ascertain deaths and any diagnosis of CRC that contributed to death or was a secondary diagnosis. **Dietary patterns definitions:** We will use 3 different approaches to define 8 dietary patterns: 4 *a priori* patterns (AHEI-2010, DASH, AMED, OMNI); 2 *a posteriori* patterns (Western and prudent); and 2 hypotheses-driven patterns (EDII, CDHR). **1. AHEI-2010:** The 11 components of the AHEI-2010 include vegetables, fruits, whole grains, sugar-sweetened beverages and fruit juice, nuts and legumes, red/processed meat, trans fat, long chain (ω -3) fats, polyunsaturated fatty acids, sodium and alcohol. We will award points for intake of each dietary component on a scale from 0-10, with 10 indicating adherence, 0 no adherence and intermediate scores categorized proportionately.¹³ **2. DASH:**^{84,85} Several different DASH scores exist,⁶ and we will use the one developed (DASH-Fung)⁸⁶ and applied by my mentors,⁶⁰ which is most commonly found in the literature with US populations. DASH-Fung scores 8 components (7 food groups and 1 nutrient)—each worth 5 points—for a total of 40 points.⁸⁶ **3. AMED:** we will use the AMED score that our group adapted for use in a US population.^{59,87} The score rewards 1 point if intake is above the cohort-specific median for vegetables, legumes, fruit, nuts, whole-grain cereals, fish, and MUFAs:SFA and 1 point for intake below the cohort-specific median for red and processed meats. In addition, alcohol intake of 5 to 10 g/d for women and 10 to 15 g/d for men received 1 point. The total score ranges between 0 and 9.^{87,88} **4. OMNI:** the OMNI diet is an improved DASH diet with partial substitution of carbohydrates with protein, about half from plant sources, or with unsaturated fat, predominantly monounsaturated fat.^{89,90} **5. Western pattern and 6. Prudent pattern:** we will derive these two *a posteriori* patterns using principal components analysis.⁹¹⁻⁹³ The factors will be rotated by an orthogonal transformation to achieve a simpler structure with greater interpretability, and the number of factors to retain will be determined using the diagram of eigenvalues.⁹¹ The factor score for each pattern will be calculated by summing intakes of food groups weighted by their factor loadings. **7. EDII and 8. CDHR:** I developed and validated these two patterns (described below) as part of my postdoctoral fellowship work. The manuscripts have been submitted.

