Statistical Analysis: The primary analysis for **Aim 1a** will prospectively assess associations between each of the 8 dietary patterns and all-cause mortality, and with incident CRC, using Cox proportional hazards regression, with separate models for men and women and in pooled analyses. For CRC, we will investigate associations by anatomic subsite (proximal colon, distal colon, rectum). After >30 years of follow-up, we have confirmed 31,286 all-cause deaths in the NHS and 12,555 in the HPFS.⁹⁴ Also, we have identified 1,764 CRC cases (823 proximal, 521 distal, and 379 rectal cancers) in NHS, and in the HPFS, we documented 1,640 CRC cases (640 proximal, 574 distal, and 426 rectal cancers).⁹⁵⁻⁹⁷ Person-time (in months) for each participant will be calculated from the date of return of the baseline questionnaire in 1980 for women and 1986 for men, until the date of death from any cause or until CRC diagnosis, or June 1, 2012 whichever came first. Cumulatively updated average dietary pattern scores will be calculated using information from all available FFQs up to the 2-year interval prior to the follow-up cycle in which death or CRC diagnosis was confirmed. We will categorize the dietary patterns into quintiles and use the lowest quintile as reference, stratifying the Cox models on calendar year, age in months, to estimate hazard ratios (HR) and 95% confidence intervals (CI) to determine risk of dying from any cause and risk of developing CRC in higher quintiles of dietary patterns. Test for trend will be performed by modeling the dietary pattern scores as continuous variable and deriving the p-value for trend from the Wald test. In multivariable analyses, we will adjust for: BMI, physical activity, age, energy intake, race/ethnicity, educational status, smoking status, family history of CRC, NSAIDs use and additionally for menopausal status and postmenopausal hormone use in women. We will assess effect modification by BMI and physical activity, and incorporate 2-6 year time lags to reduce the potential for reverse causation. Based on the magnitude of risk explained, we will select the best diet in each of the three approaches (*a priori*, *a posteriori* and hypothesis-driven) and conduct a comparative analysis to derive the overall best diet for a healthful lifestyle that maximizes CRC prevention.

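### Alcohol is scored inside AHEI-2010 and AMED but is not in the Aim 1a adjustment list, so as described it is an unadjusted potential confounder for DASH and OMNI in the a priori comparison

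*Combined protocol and SAP*

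**What the plan says.** The Rationale of Aim 1 (section C1) promises a standardised comparison of 8 dietary patterns for all-cause mortality and for CRC, "adjusting for the same set of potential confounders". The Statistical Analysis paragraph for Aim 1a gives that set: "we will adjust for: BMI, physical activity, age, energy intake, race/ethnicity, educational status, smoking status, family history of CRC, NSAIDs use". In the women's models the plan adjusts "additionally for menopausal status and postmenopausal hormone use in women". Alcohol is in neither part.

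The dietary pattern definitions in C1 treat alcohol as follows.

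- **AHEI-2010.** "The 11 components of the AHEI-2010 include vegetables, fruits, whole grains" and further items, ending in "sodium and alcohol. We will award points for intake of each dietary component on a scale from 0-10". Alcohol is one of the 11.
- **AMED.** "alcohol intake of 5 to 10 g/d for women and 10 to 15 g/d for men received 1 point". This is one of nine possible points: "The total score ranges between 0 and 9".
- **DASH.** "DASH-Fung scores 8 components (7 food groups and 1 nutrient", which are not itemised; alcohol is not mentioned.
- **OMNI.** Described only by its macronutrient substitutions; alcohol is not mentioned.
- **Western, prudent, EDII, CDHR.** Weighted sums of food groups that the plan does not list.

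The Statistical Analysis paragraph then picks the best diet within each of the three approaches according to how much risk it explains, and compares those picks to arrive at one overall best diet.

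**The concern.** Using one covariate list for every score looks like standardisation, but what a list controls depends on what each score contains. When alcohol is missing from the list, a model for a score that omits alcohol carries any confounding by alcohol. A model for a score that includes alcohol estimates the effect of a diet of which alcohol is a part. These are different quantities, and the a priori selection ranks them against each other.

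The ranking appears to rest on point estimates, so a shift of a few percent in one or two hazard ratios could change the order of diets with similar results. The selected diet is meant to inform dietary guidance for overall health and CRC prevention, so the order matters.

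**Working it through.** **1. Text check.** The four a priori scores side by side:

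| Score | Alcohol in score, as described | Alcohol in covariate list | Role of alcohol in the model |
|---|---|---|---|
| AHEI-2010 | yes, 0-10 of 110 points | no | part of the exposure |
| AMED | yes, 0-1 of 9 points | no | part of the exposure |
| DASH | none described | no | unadjusted |
| OMNI | none described | no | unadjusted |

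Shares of maximum points are 10/(11 × 10) = 9.1% for AHEI-2010 and 1/9 = 11.1% for AMED. These are shares of the score range, not of its variance or of any effect.

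Nothing elsewhere fills the gap. Alcohol is not named among the lifestyle factors assessed, the effect modifiers, the time-lag analyses or the limitations, and no alcohol sensitivity analysis is planned. Energy adjustment does not separate alcohol from other energy sources. Scoring alcohol within AMED does not adjust for amount, since intakes below and above the range both score 0.

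**2. Scale for comparison.** Table 3 gives minimum detectable associations at 80% power of 1.04 for deaths and 1.12 for CRC. The event totals agree with the text: 31,286 + 12,555 = 43,841 deaths and 1,764 + 1,640 = 3,404 CRC cases. For Q5 v Q1 with two fifths of the events, two-sided 0.05, Schoenfeld's formula gives exp{(1.960 + 0.842)/√(0.4 × events × 0.25)}:

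- deaths: exp(2.802/√4,384.1) = 1.043, in line with 1.04
- CRC: exp(2.802/√340.4) = 1.164, larger than 1.12

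Other contrasts for CRC give 1.101 (median split), 1.128 (Q5 v the rest) and 1.146 (trend). The plan does not say which contrast it used, so 1.12 serves here only as a rough scale.

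**3. Illustrative shift in the CRC hazard ratio.** The documents give no alcohol-CRC association and no alcohol intake by quintile. Assume a log-linear RR of 1.05-1.10 per 10 g/d and a 2-6 g/d difference in mean intake between Q5 and Q1 that remains after the listed covariates. The shift factor is RR^(difference/10):

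| RR per 10 g/d | Difference | Factor | ln(factor)/ln(1.12) |
|---|---|---|---|
| 1.05 | 2 g/d | 1.05^0.2 = 1.010 | 0.0098/0.1133 = 9% |
| 1.07 | 4 g/d | 1.07^0.4 = 1.027 | 0.0271/0.1133 = 24% |
| 1.10 | 6 g/d | 1.10^0.6 = 1.059 | 0.0572/0.1133 = 50% |

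If Q5 has the lower intake, the factor is the reciprocal (0.990 to 0.944).

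**4. Second set of assumptions.** Treat higher alcohol intake as binary, with prevalence 20% in Q1 and 5-30 points more in Q5, and an outcome RR of 1.1-1.5. The factor [1 + p5(RR − 1)]/[1 + p1(RR − 1)] runs from 1.025/1.020 = 1.005 to 1.25/1.10 = 1.136. The low end is negligible; the high end is as large as the Table 3 figures.

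**The case against.** The strongest reply is that alcohol belongs to AHEI-2010 and AMED as published. If it worsens their CRC result, that is a property of those diets and not bias, and adjusting the published scores for alcohol would condition on one of their own components. This stands. It is why the point concerns patterns that do not score alcohol, and why the published scores should stay primary.

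A second reply is that the inputs to the size calculation are all assumed, and that energy, smoking, BMI and education may already absorb part of any alcohol difference between quintiles. This also stands. It limits what can be said about size, but it does not show that the residual difference is nil.

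A third is that the Limitations section promises extensive multivariable adjustment for plausible confounders. That statement names no covariate, whereas the Aim 1a paragraph gives an explicit list, so it does not cure the omission.

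A reader might also infer that the whole 8-diet comparison is driven by how each diet handles alcohol. The documents do not support this. Alcohol is described in two scores. It is not mentioned for DASH or OMNI, and the food groups of the other four patterns are not listed, so alcoholic beverages may already be inside some of those scores.

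**Conclusion.** The point holds for the a priori comparison. On the plan's own descriptions, alcohol is part of the exposure for AHEI-2010 and AMED and is neither scored nor adjusted for in DASH and OMNI, and the four are ranked together. It extends to Western, prudent, EDII and CDHR only if their scores omit alcohol.

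The size is uncertain: about 1-6% on the CRC Q5 v Q1 hazard ratio under the first set of assumptions, and 0.5-13.6% under the second, broader set. Neither the size nor the direction follows from the documents. No sample-size or power figure changes.

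It is tempting to go further and say that alcohol would create a false discordance between mortality and CRC by lowering one risk and raising the other. The documents give no alcohol association with either outcome, and no mortality calculation was made here, so that reading is not supported.

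**What to change.** State for each of the 8 scores whether it contains alcohol. Add cumulatively updated alcohol intake (g/d, in categories) as a covariate in the Aim 1a mortality and CRC models for DASH, OMNI and any other pattern whose score does not include it. Keep the published AHEI-2010 and AMED as the primary scores, without alcohol as a covariate.

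Add a sensitivity comparison in which alcohol is removed from every score that contains it and all 8 models adjust for alcohol. Report whether the selected diet changes. In this comparison the covariate set is the same for every pattern, as the Rationale intends. In the primary models it will differ by the alcohol term, and the plan should say so and why.

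The cost is small. The questionnaire data are already held, and AMED already needs alcohol in g/d. The downside is a little extra analysis, and the alcohol-free scores are not the published versions, so both must be shown.

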Document Cover page

Official Title of the study: Dietary Patterns, Metabolomics and Colorectal Cancer Risk and Mortality in the Nurses' Health Study and Health Professionals Follow-Up Study

NCT number: not available

Date of the document: originally created on October 1, 2015

History of changes:

C. APPROACH

C1. Aim 1 – K99 phase: To use 3 different approaches to derive 8 dietary patterns and utilize a standardized methodology to compare the best diet for overall health with the best diet for CRC prevention; and further determine if associations with CRC prevention are mediated by biological mechanisms involving inflammation and insulin

Rationale / Preliminary data

We have previously reported that several *a priori* (AHEI, AMED or OMNI) and *a posteriori* (Western or prudent) dietary patterns are associated with overall health (with all-cause mortality as indicator)^{58,59} and with CRC prevention^{12,60} in separate studies. The current proposal goes further to determine the extent to which diets beneficial for overall health are consistent with diets beneficial for CRC prevention. This is important for designing effective dietary guidelines for overall health that are optimized for CRC prevention, given that it is not feasible to have an optimal diet for every disease. We also increase the variety of dietary patterns by including two new patterns – the EDII and CDHR derived using a third and novel approach – the hypothesis-driven approach, that combines the strengths of both *a priori* and *a posteriori* approaches.

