^athe p-value for trend is the p-value of the EDII as a continuous variable adjusted for all covariates listed in Footnote #3. ^bvalues are ratio relative concentrations, comparing highest EDII quintiles to the lowest quintile (e.g., Q5/Q1), and back transformed (e^t) since biomarker data were log transformed using natural logarithms prior to analysis; ^{c,d}fully adjusted model were adjusted for age, physical activity, smoking status, batch effects for biomarker measurements, regular aspirin/NSAID use and an inflammation-related chronic disease comorbidity score, and in NHS-II, additionally adjusted for menopausal status and postmenopausal hormone use. Chronic diseases/conditions included in the score were hypertension, cancer, diabetes, high blood pressure, heart disease, and rheumatoid/other arthritis; ^dthe overall inflammatory score was computed by summing z-scores of all four biomarkers for each participant

the 39 food groups as independent variables, and a significance level of $p=0.05$ for entry into, and retention in the model. Intakes of the food groups identified in the stepwise linear regression analyses were weighted by the beta coefficients derived from the final stepwise regression model and then algebraically summed to constitute the EDII score. Higher (more positive) scores indicate more pro-inflammatory diets while lower (more negative) scores indicate anti-inflammatory diets. The EDII is comprised of 18 food groups; 9 are anti-inflammatory and 9 pro-inflammatory. In two independent samples, the NHS-II and HPFS, the EDII significantly

predicted concentrations of several biomarkers (IL6, CRP, TNF α R2, adiponectin and an overall inflammatory marker score as construct validators) (**Table 2**).

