Preliminary study 2 - Development and validation of three indices of dietary insulinemic potential: We developed the three indices based on food groups, to assess the insulinemic potential of whole diets: 1) the empirical dietary index for hyperinsulinemia (EDIH), 2) the empirical dietary index for insulin resistance (EDIR) and 3) the composite dietary index for hyperinsulinemia and insulin resistance (CDHR). We used dietary and biomarker data (C-peptide, TG and HDL) in the NHS to develop the three indices, by fitting 2 separate stepwise linear regression models to identify the most important component food groups contributing to hyperinsulinemia (with C-peptide as the dependent variable) and to insulin resistance (ratio of TG/HDL as the dependent variable), the 39 food groups as independent variables, and a significance level of $p=0.1$ for entry into, and retention in the model. Intakes of the food groups identified in the stepwise linear regression analyses were weighted by the beta coefficients derived from the final stepwise

regression model and then algebraically summed to constitute the scores. To create the composite score, we algebraically summed up the different components of both the EDIH and the EDIR to constitute the CDHR. Higher scores on all 3 indices indicate more highly insulinemic diets (hyperinsulinemia or insulin resistance) while lower scores indicate low insulinemic or insulin sensitive diets. The EDHR comprises 24 food groups; 12 are anti-insulinemic and 12 pro-insulinemic. In the HPFS, the EDII significantly predicted concentrations of the overall insulinemic marker score (combination of C-peptide and TG/HDL) as the construct validator (**Figure 1**) and of C-peptide and TG/HDL in separate models.

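### Aim 1a names a best diet without an interval for differences between patterns or a rule for patterns that cannot be separated

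*Combined protocol and SAP*

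**What the plan says.** Aim 1 in section C1 sets out to "compare the best diet for overall health with the best diet for CRC prevention". The dietary patterns definitions add: "We will use 3 different approaches to define 8 dietary patterns". Four are a priori (AHEI-2010, DASH, AMED, OMNI), two a posteriori (Western, prudent) and two hypothesis-driven (EDII, CDHR).

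Under Statistical Analysis for Aim 1a, each pattern is related to all-cause mortality and to CRC by Cox models, "with separate models for men and women and in pooled analyses". On the contrast the plan says: "We will categorize the dietary patterns into quintiles and use the lowest quintile as reference". HRs with 95% intervals and a Wald trend test follow, one pattern at a time.

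The paragraph ends with the decision rule, "Based on the magnitude of risk explained, we will select the best diet in each of the three approaches", and a second stage that will "conduct a comparative analysis to derive the overall best diet for a healthful lifestyle that maximizes CRC prevention". The ranking metric is not defined and the second stage is not described. No section plans an interval or test for a difference between two patterns, or says what is reported when patterns are indistinguishable. Table 3 and the power section cover single associations only.

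**The concern.** The planned intervals show whether each pattern is associated with an outcome. They do not show whether one pattern does better than another. All eight are scored on the same participants, so their estimates are correlated, and the precision of a difference cannot be read from two separate intervals.

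Followed as written, the rule always yields a winner for each outcome. If the CRC winner differs from the mortality winner, the reader cannot tell a real difference from chance, yet that comparison is the stated aim. The Expected outcomes for Aim 1 then look to guidelines built on it. Because the winner is chosen for having the most extreme estimate, that estimate also tends to be exaggerated. The plan does not say which of the sex-specific or pooled models is ranked.

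**Working it through.** **Inputs from the documents.** Deaths: 31,286 + 12,555 = 43,841. CRC cases: 1,764 + 1,640 = 3,404. Both totals match Table 3. Intervals are two-sided 95%, and power is 80%.

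**Assumptions, not in the documents.**
- The metric is the quintile 5 versus quintile 1 log HR, with events spread evenly over quintiles.
- The correlation r between two patterns' log-HR estimates is 0.3 to 0.75 for a priori and hypothesis-driven patterns. It is near 0 for Western versus prudent, because the definitions specify an orthogonal rotation (approximate, since the scores are loading-weighted sums).
- The true gap between best and next best is 0.05 log HR, with 0.03 as a sensitivity.

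**1. Standard error of one log HR.** SE = sqrt(2/(D/5)) = sqrt(10/D).
- CRC: sqrt(10/3,404) = 0.0542
- Deaths: sqrt(10/43,841) = 0.0151

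The CRC value is about 3.6 times the other.

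**2. The plan's own figures.** The detectable association at 80% power is exp(2.80 × SE).
- Deaths: exp(2.80 × 0.0151) = 1.043, which agrees with Table 3's 1.04.
- CRC: exp(2.80 × 0.0542) = 1.164, against 1.12 in Table 3.

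Table 3 does not state its contrast. If 1.12 is read as quintile 5 versus 1, the implied SE is ln(1.12)/2.80 = 0.040, used below as a sensitivity.

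**3. Separating two patterns.** SE(diff) = SE × sqrt(2 − 2r). The HRs must differ by a factor of exp(1.96 × SE(diff)).

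| Outcome | r | SE(diff) | 95% factor |
|---|---|---|---|
| CRC | 0.75 | 0.0383 | 1.08 |
| CRC | 0.3 | 0.0641 | 1.13 |
| CRC | 0 | 0.0767 | 1.16 |
| Deaths | 0.75 | 0.0107 | 1.02 |
| Deaths | 0.3 | 0.0179 | 1.04 |

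If CRC were ranked within sex, the factor at r 0.75 to 0.3 would be about 1.11 to 1.20.

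**4. Two patterns, gap 0.05.** The wrong pattern ranks first with probability Φ(−0.05/SE(diff)).
- CRC: Φ(−0.78) = 0.22 at r = 0.3; Φ(−1.31) = 0.10 at r = 0.75; Φ(−0.65) = 0.26 at r = 0.
- Deaths: 0.003, under 0.001 and 0.010.

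With p and q the two outcomes' error probabilities, the winners differ with probability p(1 − q) + q(1 − p): about 22%, 10% and 26%.

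**5. Four patterns, by simulation (400,000 equicorrelated normal draws).**

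| Setting | r = 0.3 | r = 0.75 |
|---|---|---|
| Winners differ, gap 0.05, other three equal (least favourable layout) | 42% | 21% |
| Winners differ, gap 0.05, staggered in steps of 0.05 | 25% | 10% |
| Winners differ, least favourable layout, CRC SE 0.040 | 31% | 10% |
| Mortality winner wrong, gap 0.03, other three equal | 11% | 1% |

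**6. Exaggeration by selection.** If the patterns are truly equal, the selected CRC log HR is too far from the null by about 0.028-0.047 with four patterns and 0.015-0.026 with two.

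**The case against.** The strongest reply is that the selection feeds nothing later. Aim 1b analyses all eight patterns, and Aims 2 and 3 use EDII and CDHR whichever diet wins. HRs with intervals are planned for every pattern and both outcomes, and a comparative analysis is announced. This stands as a limit on reach: a reader might infer that a wrong choice would carry into the later aims, and the documents do not support that. It does not supply the missing interval, because the announced analysis has no stated contrast, interval or tie rule.

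The figures also depend on assumed gaps and correlations. At a correlation of 0.9 and a gap of 0.05, the winners would differ in only about 5% (four patterns) or 2% (two). For bivariate-normal scores, that needs score correlations of about 0.985, so I do not use it as a realistic bound. The 21-42% is the least favourable layout for a given gap, and reading Table 3's 1.12 as quintile 5 versus 1 lowers it to 10-31%. These points change the size, not the gap in the plan.

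A reader might infer that score direction is left undefined. For the hypothesis-driven indices it is not: for EDII, "Higher (more positive) scores indicate more pro-inflammatory diets", and for the insulin indices, "Higher scores on all 3 indices indicate more highly insulinemic diets". What remains is a sentence on orientation for ranking. Nor does the mismatch with 1.12 show that Table 3 is wrong, since its contrast is unstated and the table may be damaged in extraction.

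**Conclusion.** The concern holds. The selection rule has no defined metric, no interval for between-pattern differences and no provision for ties, and that does not depend on any assumed number.

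Under the stated assumptions, two CRC HRs must differ by a factor of about 1.08-1.13 (1.16 for Western versus prudent) to separate at 95%. With one pattern truly best for both outcomes by 0.05 log HR, the named winners differ in:
- about 21-42% of studies with four patterns, the other three being equal;
- about 10-25% with four staggered patterns;
- about 10-22% with two patterns;
- about 26% for Western versus prudent.

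A reader might infer that this concerns CRC alone. It is larger there because of the event counts, but the rule is equally missing for mortality, where at a gap of 0.03 the four-pattern winner is wrong in about 1-11%. Nor do the documents show that the chosen diet will be wrong; they show that the plan gives no means of telling. The harm is confined to the concluding comparison and the guideline message. The plan should be changed, but the individual pattern results are not in question.

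**What to change.** - Define the metric as one contrast: the log HR for the healthiest versus the least healthy quintile, with Western, EDII and CDHR reversed. Rank in the pooled model, show the sex-specific results and check heterogeneity by sex.
- Bootstrap participants, so that all patterns are compared on the same people, and give 95% intervals for between-pattern differences for each outcome.
- Instead of a single winner, report as a tied set all patterns whose difference from the top one has an interval including zero.
- State that the best diets for overall health and for CRC differ only if the interval for the pattern-by-outcome difference excludes zero, with simultaneous intervals for the four a priori patterns.
- Note that the selected pattern's estimate may be exaggerated by selection.

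No new data are needed; the cost is computing time and some wording. The scientific cost is that CRC will often yield a tied set. At a gap of 0.05 and correlations of 0.3 to 0.75, this happens in about 92-98% of studies with four patterns (least favourable layout) and 74-88% with two. All pattern results are still reported.
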